10.5.2 Compare the diagnostic capacity of muscle function assessment tools on undernutrition

The diagnostic capabilities of the different tools for measuring muscle function (Handgrip, gait speed, bioelectrical impedance and muscle ultrasound) will be compared by ROC curves.

10.5.3 Evaluate the association of muscle ultrasound measurements with patient morbidity and mortality

Morbidity and mortality will be compared between the groups with and without ultrasound-determined muscle function impairment, comparing length of hospital stay, mortality, and independence at discharge.

Length of hospitalization

There is a relationship between the incidence of mortality and all of the length of stay variables. Length of stay will therefore be analyzed using a competitive risk method, which takes into account the fact that patients who die are no longer eligible for length of stay analysis (26). The estimator also provides the probability of in-hospital death, so the probability of hospital discharge versus death at any time after study inclusion can be assessed simultaneously.

Mortality rate

The estimation of mortality rates will be performed by the Kaplan and Meier method. Comparison of the 2 curves will be performed by a Logrank test. The mortality rates in the 2 groups will be estimated via the survival curves.

ADL

The ADL score will be compared between the 2 groups using the discrete numerical variable comparison tests described in the general aspects.

11 Expected results in terms of scientific and professional advances

The results of this study will make it possible to verify whether ultrasound is a reliable and valid tool in the evaluation of peripheral muscle function in the context of screening for undernutrition. On the other hand, they will allow us to propose threshold values for the alteration of muscle function and to provide information on the ultrasound characteristics of the muscle in the undernourished patient and their association with the prognosis of the patient. The different tools could lead to a different estimation of the reduction of muscle mass and therefore a different prevalence of undernutrition. The results of our study will help to evaluate this and to guide professionals in the choice of tools to assess muscle function.

12 Expected benefits and risks for patients

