9.1.2 Sampling of the population

A potential of 94 patients per month eligible for this study are admitted in short stay and follow-up care and rehabilitation of diabetes-obesity, pneumology, oncology and gastro-nutrition. We anticipate a maximum inclusion of 6 patients per month for logistical reasons.

In order to obtain a representative sample of this patient population in the study, we will sample the patient population upon admission, if he/she meets the eligibility criteria and before the patient is informed and consented. The patient will be randomly assigned to either the eligible or ineligible group. Patients in the ineligible group will not be included in the study, but the number of these patients will be collected.

Patients will be sampled via a centralized random drawing system available via the internet, according to a pre-established list. This list will be programmed in advance by the study statistician. The sampling will be stratified on the care service, and unbalanced using random blocks in order to obtain a number of eligible patients of 10 per month (in order to take into account possible refusals of participation). Only the hospital's research coordinator will know the sampling list.

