9.2 Inclusion visit

The inclusion visit will take place within 48 hours of the patient's or family member's consent to participate in the study. The following data will be collected:

- Age, weight, height, BMI, gender (male/female);
- Hospitalization Service;
- Reason for hospitalization;
- Background;
- Reduced food intake or absorption;
- Inflammatory situation;
- Biological markers (albumin, pre-albumin, CRP) if applicable;
- Nutritional data (weight evolution over the last months, theoretical needs, ingestas) ;
- Mini-Nutritional Assessment Short-Form (MNA-SF);
- Autonomy Score (Katz ADL);
- Ultrasound measurements;
- Bioelectrical impedance data;
- Grip force (Handgrip);
- Walking speed.

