10.2 General aspects

Descriptive statistics will be based on means (+/- standard deviation) or medians [interquartile range] depending on the distribution of quantitative variables. Qualitative variables will be described in terms of numbers and percentages. Univariate comparisons will use the usual statistical tests after verification of the distribution of the variables (Chi2 or Fisher's test, t-test, anova or their non-parametric equivalents Wilcoxon and Kruskal-Wallis tests). Paired sample tests will be used if necessary.

Tests will be performed at the 5% significance level. The 95% confidence intervals will be provided for each estimate.

The calculations will be done using SPSS v21 IBM and R software (version 3.6.1, <http://www.R-project.org>).

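### The prognosis comparisons in section 10.5.3 are unadjusted in a cohort that mixes short-stay and rehabilitation care, so a ward difference can appear as an association with ultrasound.

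*Combined protocol and SAP*

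**What the plan says.** Section 10.5.3 divides patients into two groups by ultrasound result: "Morbidity and mortality will be compared between the groups with and without ultrasound-determined muscle function impairment". Three outcomes follow.

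- **Length of stay:** "Length of stay will therefore be analyzed using a competitive risk method". No covariate or stratum is named.
- **Mortality:** Kaplan-Meier curves, and "Comparison of the 2 curves will be performed by a Logrank test".
- **Discharge autonomy:** "The ADL score will be compared between the 2 groups using the discrete numerical variable comparison tests described in the general aspects".

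The general aspects (section 10.2) add only that "Univariate comparisons will use the usual statistical tests after verification of the distribution of the variables". No regression model appears anywhere in section 10. Sections 10.3.1 and 10.3.2 point to a special treatment in a section 11.4, which does not exist. The matching text is in 10.5.3, and it handles death as a competing event but contains no adjustment.

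Section 5.1 admits patients from short-stay and from follow-up and rehabilitation care in four specialties. Section 10.3.1 counts the stay in the inclusion service. Section 9.1.2 says of recruitment that "The sampling will be stratified on the care service, and unbalanced using random blocks". Section 9.2 records "Age, weight, height, BMI, gender (male/female"), the hospitalization service and a baseline Katz ADL score. None of these enters the prognosis analysis.

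**The concern.** Short-stay and rehabilitation wards have different purposes, so their lengths of stay are likely to differ whatever the patient's muscle status. If impairment is also more frequent in one type of ward, the impaired group contains more of that ward's patients and takes on its length of stay. A crude comparison cannot separate the two. Discharge ADL and mortality are open to the same problem, and discharge ADL is also compared without the ADL score at inclusion.

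At stake is the interpretation of this objective. Section 11 lists the association of ultrasound findings with prognosis among the expected results. A difference that comes from ward mix could be read as information about the ultrasound measurement.

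**Working it through.** **1. The plan's own figures.** The documents give no sample size, power or expected number of events for the prognosis comparisons. The 118 comes from the reproducibility calculation in section 10.1 (ρ₀ = 0.70, ρ₁ = 0.80, k = 2, α = 0.05, power 80%). With θ = ρ/(1−ρ) and C₀ = (1+kθ₀)/(1+kθ₁):

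- θ₀ = 0.70/0.30 = 2.333; θ₁ = 0.80/0.20 = 4
- C₀ = 5.667/9 = 0.630; (ln C₀)² = 0.214
- N = 1 + 2(1.645+0.842)² × 2 / (0.214 × 1) ≈ 116.6, so 117 with one-sided α (148 two-sided)

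This is within one patient of 118. It does not involve prognosis, so adjusting the prognosis analysis leaves it unchanged.

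**2. Inputs for the illustration.** From the documents: n = 118, mean stay about 30 days (section 6.3), overall impairment 45–60% (section 10.1). Assumed, because the documents give nothing by service: one third of patients in short-stay and two thirds in rehabilitation care, exponential stays, no deaths, and the ward-level means and impairment rates shown below. Every pair of means averages 30 days; for example, 10/3 + 2×40/3 = 30.

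**3. Spurious difference in mean stay, with no effect within wards (means 10 and 40 days).**

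- Impairment 40% v 60%: the impaired share is 0.133 + 0.400 = 0.533 and their mean is (0.133×10 + 0.400×40)/0.533 = 32.5 days. The unimpaired share is 0.200 + 0.267 = 0.467 and their mean is (0.200×10 + 0.267×40)/0.467 = 27.1 days. Difference: about 5 days.
- Impairment 35% v 65%: (0.117×10 + 0.433×40)/0.550 = 33.6 days, against (0.217×10 + 0.233×40)/0.450 = 25.6 days. Difference: about 8 days.

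**4. Rejection rate of the crude 5% log-rank test on time to discharge** (simulation, 3,000–4,000 runs per scenario, no true effect within wards):

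| Mean stay, short-stay / rehabilitation (days) | Impairment, short-stay v rehabilitation | Crude test |
|---|---|---|
| any of the pairs | equal | about 5% |
| 25 / 32.5 | 40% v 60% | about 6% |
| 20 / 35 | 45% v 55% | about 6% |
| 20 / 35 | 40% v 60% | about 8% |
| 10 / 40 or 15 / 37.5 | 45% v 55% | about 7% |
| 15 / 37.5 | 40% v 60% | about 11% |
| 15 / 37.5 | 35% v 65% | about 19% |
| 10 / 40 | 40% v 60% | about 15% |
| 10 / 40 | 35% v 65% | about 27% |

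Stratified by ward type, the test rejects in about 5–6% of runs. The excess appears only when wards differ in both impairment and stay.

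**5. Mortality.** Assume four equal services with impairment 35/45/55/65% and death risks 2/5/8/15%, and no effect within any service. The crude risk in impaired patients is (0.35×2 + 0.45×5 + 0.55×8 + 0.65×15)/2 = 8.6%. In unimpaired patients it is (0.65×2 + 0.55×5 + 0.45×8 + 0.35×15)/2 = 6.5%. The spurious risk ratio is 1.33. Room to adjust is small: an assumed in-hospital mortality of 3–15% gives 118 × 0.03 ≈ 4 to 118 × 0.15 ≈ 18 deaths.

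**6. Cost of stratifying when strata are unrelated to outcome.** For a true mean-stay ratio of 1.7, log-rank power is about 80% unstratified, about 79% with two strata, and about 71% with eight (four specialties × two care types, 118/8 ≈ 15 patients per stratum).

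**The case against.** The best defence is that the objective is worded as an association. The plan nowhere claims independent prediction, and an unadjusted comparison answers the question as written. That stands as far as description goes, and labelling the results as unadjusted would meet part of the point. It does not remove the need for an adjusted analysis, because an association produced by ward mix says nothing about ultrasound.

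A second objection is that the size is unknown. This is correct: mild ward differences, equally consistent with a 30-day mean, give 5–8%, so material inflation is possible but not shown.

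A reader might infer three stronger things that the documents do not support:

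- **That sampling by service causes the confounding.** Section 9.1.2 stratifies to obtain a representative sample. Any bias would come from differences between services, not from the sampling.
- **That a single ultrasound threshold places too many women in the impaired group.** The impedance thresholds are sex-specific, but no ultrasound threshold is stated, so this is conjecture. Sex is a reasonable covariate without it.
- **That the primary conclusions are at risk.** Reliability and diagnostic accuracy do not use these comparisons.

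Also, discharge ADL is scored before a scheduled discharge (section 10.3.3). Patients who die or leave unexpectedly may lack it, so 118 observations cannot be assumed for that outcome.

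**Conclusion.** The omission is real and should be corrected, as a matter for a secondary objective. Section 10 specifies only crude comparisons in a cohort whose services plausibly differ in stay and may differ in impairment. Under the assumptions shown, the false-positive rate for length of stay ranges from about 5% (equal or nearly equal impairment, or similar stays) to about 27% (means of 10 and 40 days, impairment 35% v 65%). Stratification holds it at about 5–6%.

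These figures are illustrative. They rest on an assumed ward mix, assumed ward means and impairment rates, exponential stays and no deaths. More extreme inputs give larger values: four services with median stays of 15–50 days and impairment of 20–80% give 75%. Nothing in the documents supports that spread, and it should not be read as the expected error. The gain from adding specialty, age and sex was not simulated.

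**What to change.** Amend section 10.5.3 as follows.

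- **Length of stay:** stratify the competing-risk comparison by short-stay versus rehabilitation (two strata), with specialty, age and sex as covariates. Confirm that the hospitalization service field in the e-CRF separates the two care types; section 9.2 does not say that it does.
- **Discharge ADL:** use a regression on impairment group adjusted for baseline Katz ADL, care type, age and sex. State how patients without a discharge score are handled.
- **Mortality:** keep the crude log-rank test, add stratification by care type only if events permit, and otherwise label the result unadjusted.
- **Reporting:** present all crude comparisons as descriptive, and correct the references to section 11.4.

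The cost is SAP wording and possibly one e-CRF field. No extra patients are needed. There is a small loss of precision if service proves unrelated to outcome. It is larger with all eight service cells as strata (power about 80% to 71% in the check above), so two strata are preferred. Writing this down before the data are seen also avoids a later choice of adjustments.

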4.2 Secondary endpoint

Secondary endpoints will be:

- Correlation measurements of muscle ultrasound with:
 - Bioelectrical impedance;
 - Handgrip;
 - Walking speed.
- Comparison of the diagnostic accuracy in undernutrition of muscle ultrasound with those of :
 - Bioelectrical impedance;
 - Handgrip;
 - Walking speed.
- Measure of association of muscle ultrasound measurements with patient morbidity and mortality:
 - Length of hospitalization (days);
 - Mortality: proportion and date of occurrence of death among patients included during hospitalization;
 - Autonomy at discharge: Activities Daily Living (ADL) score, **Appendix 1**.

5 Eligibility Criteria

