9.3 Follow-up visit

A follow-up visit will be conducted daily to collect the patient's vital status and to verify if a discharge or transfer is planned. In the event of discharge or transfer, the following data will be collected:

- Length of hospitalization (in days);
- Vital status (death yes/no) ;
- Autonomy score (Katz ADL).

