10.3.2 Mortality

Number of deaths out of the total number of patients included. A specific statistical treatment (**described in section 11.4**) will be performed on the mortality rate.

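### In-hospital mortality is read from Kaplan–Meier curves with no horizon and no rule for live discharge; if discharge is censored, the rate overstates the cumulative incidence of in-hospital death at the same day

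*Combined protocol and SAP*

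**What the plan says.** - **Endpoint (section 4.2).** "Mortality: proportion and date of occurrence of death among patients included during hospitalization".
- **Definition (section 10.3.2).** "Number of deaths out of the total number of patients included". The section then refers to a specific treatment in section 11.4. No such section exists, so 10.5.3 holds the only mortality analysis text.
- **Observation (sections 9.3 to 9.5).** Vital status is checked daily in hospital. "In the event of discharge or transfer, the following data will be collected": length of stay, vital status and Katz ADL. The last visit is at discharge or death, and nothing is planned after that.
- **Mortality analysis (section 10.5.3).** The estimator is named first: "The estimation of mortality rates will be performed by the Kaplan and Meier method". For the contrast between groups, the plan adds: "Comparison of the 2 curves will be performed by a Logrank test". On where each group's figure comes from, it says: "The mortality rates in the 2 groups will be estimated via the survival curves". There is no time point and no rule for live discharge, definitive transfer or withdrawal.
- **Length-of-stay analysis (same section, the paragraph before).** "Length of stay will therefore be analyzed using a competitive risk method", and "The estimator also provides the probability of in-hospital death".
- **Time frame.** Section 10.5.3 counts from study inclusion, while section 10.3.1 counts stay in the inclusion service from admission. Section 6.3 describes follow-up over the whole stay in the care unit, about 30 days on average, but also lists participation as 30 days.

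**The concern.** A patient who has gone home can no longer die in hospital, so for this endpoint live discharge is a competing event. Kaplan–Meier with discharge censored treats discharged patients as if they still faced the in-hospital death hazard. The resulting 1 − KM is never below the cumulative incidence at the same horizon, and exceeds it once a death follows a discharge.

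The plan does not say that discharge is censored. With no vital status after discharge, however, an analyst following section 10.5.3 would most likely do so. The report could then carry a figure labelled as the mortality rate that differs from the probability of in-hospital death given by the length-of-stay analysis, with nothing to say which one governs. The logrank test would compare death hazards per day in hospital, which is not always a comparison of the proportions who die.

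**Working it through.** **Inputs.** Mean stay 30 days (section 6.3). Cohort of 118 (section 10.1), used here only as a cohort size. Whole-stay mortality *m* is not in the documents, so 2%, 5% and 10% are assumed. The documents state no mortality figure that could be reproduced.

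**Step 1: formulas.** With constant hazards, the exit hazard is 1/30 per day and the death hazard *m*/30.
- Discharge censored: 1 − KM(t) = 1 − exp(−*m*t/30).
- Discharge as competing event: CIF(t) = *m*(1 − exp(−t/30)).
- Still in hospital: 118·exp(−t/30), which is 43.4 at day 30 and 16.0 at day 60.

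Example for *m* = 10%, day 30: 1 − exp(−0.10) = 0.0952, against 0.10 × (1 − exp(−1)) = 0.0632.

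**Step 2: results.**

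| *m* | Day 30: 1 − KM | Day 30: CIF | Day 60: 1 − KM | Day 60: CIF |
|---|---|---|---|---|
| 2% | 2.0% | 1.3% | 3.9% | 1.7% |
| 5% | 4.9% | 3.2% | 9.5% | 4.3% |
| 10% | 9.5% | 6.3% | 18.1% | 8.6% |

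The ratio is about 1.5 to 1.6 at day 30 and 2.1 to 2.3 at day 60.

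**Step 3: less variable stays.** With gamma stays of mean 30 days and the death hazard a fixed share *m* of the exit hazard, 1 − KM = 1 − S(t)^*m* and CIF = *m*(1 − S(t)). For *m* = 10% at day 30 this gives 8.6% against 5.9% (shape 2) and 8.0% against 5.7% (shape 4). The gap narrows but remains.

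**Step 4: against whole-stay deaths over patients included.** That proportion is *m* itself. At day 30, 1 − KM (2.0%, 4.9%, 9.5%) is close to it or slightly below. Under constant hazards it passes *m* when t > −30·ln(1 − *m*)/*m*, that is after day 30.3, 30.8 and 31.6 for the three values. At the end of the curve (1,000 simulated cohorts of 118, exponential stays), 1 − KM averaged 10%, 23% and 42%, with medians of 5%, 16% and 35%. The competing-risk estimate equalled the crude proportion in every run. The missing horizon therefore matters as much as the missing censoring rule.

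**Step 5: the test.** Death hazard per day is *m* divided by mean stay. With 10% mortality in both groups and stays of 40 and 20 days, the hazards are 0.0025 and 0.0050, a ratio of 0.5. With 10% against 5% and the same stays, both are 0.0025, a ratio of 1.0. Rejection rates at two-sided 5% follow (4,000 simulated trials, 59 per group, exponential stays, whole stay observed). Gray-type means a logrank that keeps discharged patients at risk. The first group listed is the one with the longer stay.

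| Mortality | Mean stays (days) | Logrank | Gray-type |
|---|---|---|---|
| 10% / 10% | 30/30 | 5.8% | 5.5% |
| 10% / 10% | 33/27 | 6.1% | 4.4% |
| 10% / 10% | 36/24 | 11.5% | 5.2% |
| 10% / 10% | 40/20 | 22.3% | 4.8% |
| 10% / 5% | 30/30 | 16.0% | 16.5% |
| 10% / 5% | 33/27 | 8.7% | 16.4% |
| 10% / 5% | 40/20 | 4.9% | 15.2% |

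With equal stays the two tests agree. If observation were cut at 30 days, the 40/20 rows become 16.1% against 8.1% (equal mortality) and 4.2% against 6.2% (10% against 5%), so the advantage of the Gray-type test depends largely on observing the whole stay.

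**The case against.** The best defence is that no section says discharge is censored. If discharged patients stay in the risk set as alive to a fixed horizon, 1 − KM equals the proportion dying in hospital by that horizon and there is no bias. Section 10.3.2 already gives the crude proportion, section 10.2 already plans Chi2 or Fisher tests and 95% confidence intervals, and section 10.5.3 already yields the competing-risk probability, so correct figures would stand beside the Kaplan–Meier one. The outcome is secondary, and the day-30 gap is smaller than sampling error (12 deaths in 118: exact 95% CI 5.4% to 17.1%).

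Most of this stands, and it rules out three stronger readings that a reader might infer:
- *That the Kaplan–Meier rate is certainly inflated and must disagree with the other two figures.* This depends on an unstated censoring rule. Even under that rule, the day-30 value is not above whole-stay deaths over patients included.
- *That the logrank test is invalid.* It is a valid test of the cause-specific death hazard. It departs from a comparison of mortality proportions only if stays differ between groups, and no section supports any particular difference.
- *That Gray's test is required.* The stated objective is an association with mortality, and a correctly labelled logrank can serve it.

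What does not fall is the gap itself. The plan reads a rate off a curve without saying at which day or how the commonest exit is treated, while the estimator in the preceding paragraph needs no such repair. Unlike sampling error, the bias under censoring is systematic and can be removed without more data.

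**Conclusion.** The point holds in conditional form. Section 10.5.3 leaves the horizon and the handling of live discharge open. Under the likely default of censoring at discharge, 1 − KM overstates the cumulative incidence of in-hospital death at the same horizon: by 0.7, 1.7 and 3.2 percentage points at day 30, and by roughly 2, 5 and 10 points at day 60, for assumed whole-stay mortality of 2%, 5% and 10%. These sizes rest on constant hazards and the 30-day mean stay; the mortality rates are illustrations, not protocol figures, and the day-60 values rest on about 16 of 118 patients still in hospital. The effect on the test is a possibility that depends on unequal stays, not an established fault. Importance is minor to moderate: it should be corrected, but no sample-size decision depends on it.

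**What to change.** Rewrite the mortality paragraph of section 10.5.3, for example:

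> In-hospital mortality in each group will be estimated by the cumulative incidence function, with live discharge as the competing event, using the estimator planned for length of stay. Deaths over patients included will be reported per group with 95% CI. Groups will be compared by Gray's test.

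Keeping the logrank in place of Gray's test is acceptable if it is labelled a comparison of cause-specific death hazards. Mortality rates should not be quoted from Kaplan–Meier curves that censor discharge.

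Then settle:
1. One time origin: inclusion (10.5.3) or admission (10.3.1).
2. One observation window. Sections 6.3 and 10.3.1 point to the stay in the inclusion service; say whether the 30 days of participation in 6.3 is an average or a cut-off.
3. Definitive transfer and withdrawal. One option is to count definitive transfer as live discharge, since section 9.3 collects the same data for both, and to censor at withdrawal. Temporary transfers are already excluded as discharges by 10.3.1.
4. The references to section 11.4 in 10.3.1 and 10.3.2, which should point to 10.5.3.

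The cost is about one paragraph and two cross-references, with R already planned and no added patients or procedures. The e-CRF must hold the type and date of exit. The rule should be fixed before the data are analysed, so that the mortality figure is not chosen afterwards.

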10.3.3 Katz Activities Daily Living (ADL) Score

The Katz ADL score ([Appendix 1](#)) is completed within 48 hours prior to (scheduled) hospital discharge by the patient's caregiver or nurse. The total score is out of 6. A score of less than 3 indicates major dependence, a score of 0 indicates total dependence.

The Katz ADL score will be treated as a discrete numerical variable.

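### Discharge Katz ADL is compared without the Katz ADL collected at inclusion, so the result cannot show whether ultrasound adds prognostic information beyond autonomy at inclusion

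*Combined protocol and SAP*

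**What the plan says.** The endpoint in section 4.2 is "Autonomy at discharge: Activities Daily Living (ADL) score". Section 10.5.3 sets the grouping: "Morbidity and mortality will be compared between the groups with and without ultrasound-determined muscle function impairment". For ADL it then states: "The ADL score will be compared between the 2 groups using the discrete numerical variable comparison tests described in the general aspects".

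Section 10.2, to which this refers, says "Univariate comparisons will use the usual statistical tests after verification of the distribution of the variables" and lists the t-test, ANOVA, Wilcoxon and Kruskal-Wallis tests for numerical variables. Its only further provision is "Paired sample tests will be used if necessary".

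Katz ADL is recorded twice. Section 9.2 lists it at inclusion together with the ultrasound measurements, and says of that visit: "The inclusion visit will take place within 48 hours of the patient's or family member's consent to participate in the study". Sections 9.3 and 9.4 list it again at the end of the stay, and the table in 9.5 ticks both visits. Under section 10.3.3 the score "is completed within 48 hours prior to (scheduled) hospital discharge", has a maximum of 6, and is treated as a discrete numerical variable.

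No section uses the inclusion score as a covariate, in a change score or in any model.

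**The concern.** Nothing in the design balances the two ultrasound groups on autonomy at the time of the scan, and the protocol's rationale gives reason to expect imbalance. Section 1.2 ties muscle mass to functional capacity and autonomy. Section 1.4 reports a linear relation between grip strength and Katz disability. Section 1.5 links reduced muscle thickness or area to loss of strength. On those premises, impaired patients would tend to be more dependent when they are scanned.

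Sections 2 and 11 say that the study will inform on how ultrasound characteristics relate to the patient's prognosis. A discharge difference that was already there at inclusion is weak support for that message: it would show that ultrasound tracks current dependence, not that it adds anything to a Katz score taken at the same visit. The raw comparison cannot tell these two situations apart. Precision may be lost as well, since the inclusion score probably explains part of the variation at discharge.

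**Working it through.** **The plan's own figure.** The documents give no sample size, SD, effect size or correlation for ADL. The total of 118 comes from the reliability calculation in section 10.1 (ICC 0.80 against 0.70, k = 2, alpha 0.05, power 80%):

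- C0 = (1 + 2×0.7/0.3)/(1 + 2×0.8/0.2) = 5.667/9 = 0.630, so (ln C0)² = 0.214.
- N = 1 + 2(1.645 + 0.842)²×2/0.214 = 116.6, or 117 with one-sided alpha, against 118 stated.

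The figure reproduces to within one patient, but it says nothing about ADL.

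**Inputs for the ADL check**

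- From the documents: N = 118 and a 5% test level (taken as two-sided). The expected 45% to 60% with muscle impairment (10.1) serves as the range for the group split; 59 per group is used below unless stated.
- Assumed: r, the within-group inclusion-discharge correlation, from 0.3 to 0.9; d0, the inclusion gap between groups, from 0 to 0.8 SD; equal SDs; a discharge score for all 118 patients.

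**Carry-over.** If ultrasound adds nothing beyond inclusion ADL, the expected raw discharge difference is r×d0. Its standard error is √(2/59) = 0.184 SD. For r = 0.7 and d0 = 0.5 the difference is 0.35 SD and the ratio is 0.35/0.184 = 1.90, so about 48% of studies would be significant. Over the range, the share of studies with a significant unadjusted test is:

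| d0 (SD) | r = 0.3 | r = 0.5 | r = 0.7 | r = 0.9 |
|---|---|---|---|---|
| 0.25 | 6% | 10% | 16% | 23% |
| 0.5 | 13% | 27% | 48% | 69% |
| 0.8 | 26% | 58% | 86% | 97% |

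At d0 = 0 the rate is the nominal 5%.

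Because the Katz score is bounded and moves in half-point steps, the d0 = 0.5 row was checked by simulation on a 0-6 scale with those steps (assumed centre 4.5, SD 1.5). The unadjusted Wilcoxon test was significant in 12%, 28%, 43% and 67% of runs. A linear model adjusted for inclusion ADL was significant in 5% to 6%.

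**Precision.** The variance of the adjusted difference relative to the unadjusted one is (1 − r²)[1 + p(1 − p)d0²], where p is the share impaired. With p = 0.5:

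| d0 (SD) | r = 0.3 | r = 0.5 | r = 0.7 | r = 0.9 |
|---|---|---|---|---|
| 0 | 0.91 | 0.75 | 0.51 | 0.19 |
| 0.5 | 0.97 | 0.80 | 0.54 | 0.20 |
| 0.8 | 1.06 | 0.87 | 0.59 | 0.22 |

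With balanced groups and 45% to 60% impaired, the difference detectable with 80% power falls from 0.52-0.53 SD unadjusted to 0.49-0.50 SD at r = 0.3 and 0.37-0.38 SD at r = 0.7. With d0 = 0.8 and r = 0.3 there is no gain.

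**The case against.** The strongest reply is that the planned test answers the stated question. The objective is association with autonomy at discharge, and an unadjusted comparison estimates that validly. Value beyond inclusion autonomy is a different quantity, and no objective names it. This stands: the plan is incomplete for a claim about prognosis, but the analysis is not wrong.

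Second, muscle loss that predates admission may already have lowered the inclusion score. Adjusting would then remove part of the association of interest, and recording both at the same visit does not rule this out. This also stands, and it is why both estimates are needed.

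Third, a reader might infer that the discharge result will mostly restate the inclusion difference. That would need a large gap and a strong correlation, and the documents supply neither.

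Fourth, a reader might infer a large and certain gain in precision. Correlations of 0.6 to 0.8 would make 118 patients worth 118/0.64 = 184 to 118/0.36 = 328, and at r = 0.7 would raise power for a 0.5 SD effect from about 77% to about 97%. Those figures assume no inclusion gap, whereas the carry-over argument assumes one. With d0 = 0.5 and r = 0.7, a raw difference of 0.5 SD becomes 0.5 − 0.35 = 0.15 SD after adjustment. Its standard error is 0.184×√(0.51×1.0625) = 0.136 SD, and power is about 20%. The two benefits cannot both be claimed at full size.

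The provision for paired tests does not answer the point, because a paired test does not adjust a comparison between two groups.

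**Conclusion.** The point holds in a limited form. As written, the ADL analysis cannot separate a difference already present at inclusion from information that ultrasound adds about autonomy at discharge, although the score needed to do so is collected. If ultrasound adds nothing and the inclusion gap is 0.5 SD, a significant raw result appears in about 13% to 69% of studies as r runs from 0.3 to 0.9; with no gap there is no carry-over. A precision gain is likely at moderate or high r, but it is not guaranteed. All of these sizes rest on assumed values of r and d0, on near-equal groups and on complete discharge scores; deaths would reduce the number analysed.

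The covariate is an inclusion value, taken within 48 hours of consent, and not strictly an admission value.

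The documents do not support the reading that the unadjusted comparison is invalid, or that its result would be mainly an inclusion effect. The matter concerns one secondary endpoint and leaves the sample size and the primary analysis unchanged.

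**What to change.** In section 10.5.3, keep the unadjusted comparison and add a regression of discharge Katz ADL on ultrasound group with inclusion Katz ADL as covariate. Choose in advance between a linear model and an ordinal one; the bounded 0-6 score is a reason to consider the ordinal model. Report both estimates side by side with 95% confidence intervals.

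State how each will be read: the unadjusted result as association with discharge autonomy, the adjusted result as information beyond autonomy at inclusion. State also that both apply to patients discharged alive, since the ADL paragraph gives no rule for deaths and section 10.3.3 ties the score to a scheduled discharge.

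The cost is a short addition to one section. It needs no new data, visits or patients, so it is a free improvement.
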